## 5. STUDY PROCEDURES

### 5.1 Screening (Visit 1)

The following procedures are performed during screening, staging and workup. These procedures are to be performed within 4 weeks prior to study drug administration, except where indicated.

A signed and dated IEC/IRB approved informed consent form must be obtained before any study specific procedures are performed. Procedures that are part of routine care are not considered study specific procedures. All subjects will be screened for eligibility before enrollment. Once the subject has met all inclusion criteria, they will be enrolled onto the study.

Table 5.1: Procedures during Screening, Staging and Workup

Procedures	Specifics
Informed consent	
Full History and Physical Examination	History – present illness, prior surgeries, other medical illnesses, review of systems, allergies, prior therapy for cancer and concurrent meds;  Physical exam – record weight, and note abnormalities in any major organ system (including but not limited to neurologic, head and neck, lymph nodes, cardiovascular, pulmonary, abdomen, extremities), note and measure sites of disease
Concomitant Medications	
Vital signs (including temperature, pulse, and blood pressure)	
ECOG performance status	
Urine or blood pregnancy test (females of child-bearing potential only)	Within 7 days prior to first dose
Disease status (IPSS classification and WHO disease classification)	Staging with bone marrow aspiration and/or biopsy for disease assessment.
Note: Bone marrow aspirate and/or biopsy within 4 weeks prior to first dose of drug in all patients. Cytogenetics and	

immunohistochemistries performed as indicated.	
Serum chemistries and iron studies (repeat if screening chemistries completed greater than 72 hours prior to the first dose)	Sodium, potassium, blood urea nitrogen, creatinine, glucose, calcium, phosphate, magnesium, AST and/or ALT, total bilirubin, alkaline phosphatase, uric acid, serum iron, transferrin, transferrin saturation, total iron binding capacity and ferritin.
CBC with differential (repeat if screening test completed greater than 72 hours prior to the first dose)	Differential may be omitted if WBC $\leq 0.5 \times 10^9/L$

## 5.2 On-Study Procedures

PROCEDURES	Pre-Study Screen o	Cycle 1 Day 1	Cycle 1 Day 8 (+/- 2 days)	Cycle 1 Day 15 (+/- 2 days)	Cycle 1 Day 22 (+/- 2 days)	Day 1 Cycle 2 onwards (+/- 5 days)	End of Treatment Visit (+/- 5 days)	Safety Visit 28 days after last dose (+/- 28 days)
Informed Consent	X							
Eligibility	X	X						
Medical History	X							
Patient Weight	X							
Vital Signs	X	X	X	X	X	X	X	X
Physical Exam and Performance Status	X	X				X	X	X
Concomitant Medications	X	X	X	X	X	X	X	X
Transfusion and Supportive Care Assessment	X	X	X	X	X	X	X	X
CBC with differential	X*	X	X	X	X	X 	X	X 
Blood Chemistries (AST, ALT, bilirubin)	X** a	X	X	X	X	X 	X	X
12-lead EKG	X a							
Bone marrow aspiration and/or biopsy	X					X 	X	
IPSS score & WHO disease classification	X					X 	X	
Pregnancy Test	X†							
Investigational Drug Dispense		X				X		
AE and SAE assessment	X	X	X	X	X	X	X	X
Optional: Correlative studies 	X							

oScreening must be performed within 4 weeks prior to study drug initiation / study start unless otherwise indicated

\*CBC with differential and blood chemistries including iron studies (sodium, potassium, BUN, creatinine, glucose, calcium, phosphate, magnesium, AST, ALT, total bilirubin, alkaline phosphate, uric acid, serum iron, transferrin, transferrin saturation, total iron binding capacity and ferritin) must be performed within 72 hours of Cycle 1 Day 1

^Serum iron, transferrin, transferrin saturation, total iron binding capacity and ferritin are required only on Cycle 1 Day 1 and do not need to be repeated

aEKG, including QTc intervals, at screening or baseline. A follow-up EKG will be performed if a subject experiences a clinically relevant abnormality.

†Within 7 days of Day 1 in females of child-bearing potential

Weekly CBC with differential and blood chemistries required until stable counts, and weekly x4 weeks after any change in eltrombopag dosing

Weekly CBC with differential should be performed weekly for the 4 weeks after discontinuation of eltrombopag

Bone marrow aspiration and/or biopsy with cytogenetics required for study entry, and every cycle for the first 4 cycles for primary outcome, and then every 3 cycles as clinically indicated. Cytogenetics do not need to be repeated if normal at study start.

Optional correlative studies will be performed on bone marrow sample taken at screening. The studies will include an analysis of mutational status of up to 53 genes known to be affected in acute leukemias as well as gene expression profiling, and evaluation of any potential relationship with the presence or absence of mutations and response will be assessed.

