### **4.2. Study Duration**

4.2.1. All subjects must complete a screening visit, day 1 visits for each new cycle, an end of treatment visit and whenever possible, an end of study safety visit 28 days after the last dose of eltrombopag.

4.2.2. Treatment will continue until discontinuation due to relapse, unacceptable toxicity, or disease progression as defined by the IWG 2006 criteria for MDS. This includes:

- clinically significant progressive disease at any time, or

- a lack of clinical benefit after 4 cycles of treatment at the highest dose of study medication, or
- Possibility of undergoing allogeneic stem cell transplantation
- discontinuation of study drug for more than 6 weeks, or
- intercurrent illness that prevents further administration of treatment, or
- unacceptable adverse event(s), or
- patient decision for study withdrawal, or
- general or specific changes in the patient's condition that render the patient unacceptable for further treatment in the judgement of the investigator

4.2.3. Study cycles will be administered every 28 days  $\pm$  5 days or upon resolution of any clinically significant study drug related AE to grade 0-1, whichever occurs first. If a subsequent cycle is delayed due to adverse events related to decitabine, or if it is considered in the best interest of the patient to delay administration of decitabine (e.g. because of concern for an infection), administration of the eltrombopag may continue as planned.

4.2.4. Administration of subsequent cycles should be administered when neutrophils recover to  $\geq 1 \times 10^9/L$  and platelets to  $\geq 30 \times 10^9/L$  or to baseline levels prior to the start of the last cycle of therapy. Patients with residual disease may start the next cycle with neutrophil and/or platelet counts lower than these if judged to be in the best interest of the patient to start the next cycle. The decision to treat should be documented in the patient's medical record.

4.2.5. Patients may remain on study for up to 12 cycles if the patient demonstrates clinical benefit and no excessive toxicity (i.e. no clinically significant study-drug related grade  $\geq 3$  toxicity). Patients who are experiencing clinical benefit and have not experienced excessive toxicity may be eligible to continue therapy after discussion with the PI and the discussion documented in the patient's medical record.

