### 5.3. End of Study Visit:

Subjects will undergo an End of Treatment Visit at the time of discontinuation of eltrombopag. A bone marrow biopsy and/or aspirate with cytogenetics for IPSS and WHO classification will be performed at this visit. Cytogenetics can be omitted if diploid at study start.

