### 5.4. Safety Visit:

Whenever possible, subjects will undergo an End of Study Safety Visit 4 weeks after his/her last dose of investigational product in the treatment period.

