Only unexpected AEs will be recorded in the Case Report Form (CRF). The Principal Investigator will sign and date the PDMS or CORE Case Report Form toxicity pages per each patient at the completion of each course. Following signature, the Case Report Form will be used as source documentation for the adverse events for attribution.

**All life-threatening or fatal events**, that are unexpected, and related to the study drug, must have a written report submitted within **24 hours** (next working day) of knowledge of the event to the Safety Project Manager in the IND Office.

**Unless otherwise noted, the electronic SAE application (eSAE) will be utilized for safety reporting to the IND Office and MDACC IRB. MDACC.**

**Serious adverse events will be captured from the time of the first protocol-specific intervention, until 30 days after the last dose of drug unless the participant withdraws consent. Serious adverse events must be followed until clinical recovery is complete and laboratory tests have returned to baseline, progression of the event has stabilized, or there has been acceptable resolution of the event.**

**Additionally, any serious adverse events that occur after the 30 day time period that are related to the study treatment must be reported to the IND Office. This may include the development of a secondary malignancy.**

The following SAEs are not subject to expedited reporting, but would still be included in the annual report via the SAE log.

- a. Infection or cytopenias leading to hospitalization or prolongation of hospitalization  
Disease progression leading to death, life-threatening AE, hospitalization or prolongation of hospitalization, or disability.

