#### **6.2.2.3. SAE Reporting to Study Supporter ( Novartis Oncology)**

Any serious adverse events which occur during the clinical study or within 30 days of receiving the last dose of study medication, whether or not related to the study drug, must be reported by the investigator. In addition, any SAEs which occur as a result of protocol specific diagnostic procedures or interventions must also be reported.

All serious adverse events must be reported by facsimile within 24 hours to Novartis Oncology . MDC – Oncology [contact] (make sure you include the 1 prior to the 610 as this is a desktop fax)

The SAE report should comprise a full written summary, detailing relevant aspects of the adverse events in question. Where applicable, information from relevant hospital case records and autopsy reports should be included. Follow-up information should be forwarded to Novartis Oncology within 24 hours.

SAEs brought to the attention of the investigator at any time after cessation of eltromboapg and considered by the investigator to be related or possibly related to eltrombopag must be reported to Novartis Oncology if and when they occur. Additionally, in order to fulfill international reporting obligations, SAEs that are related to study participation (e.g., procedures, invasive tests, change from existing therapy) or are related to a concurrent medication will be collected and recorded from the time the subject consents to participate in the study until he/she is discharged.

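### The ±28-day window on the 28-day safety visit runs from day 0 to day 56, so the visit can coincide with the End of Treatment visit and add no post-treatment observation

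*Combined protocol and SAP*

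**What the plan says.** The schedule of assessments in section 5.2 heads its final column "Safety Visit 28 days after last dose (+/- 28 days". The items ticked there are vital signs, physical examination and performance status, concomitant medications, transfusion and supportive care, CBC, blood chemistries (AST, ALT, bilirubin), and AE/SAE assessment.

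Two text sections describe the same visit. Section 4.2.1 asks for "an end of study safety visit 28 days after the last dose of eltrombopag", and section 5.4 says that "subjects will undergo an End of Study Safety Visit 4 weeks after his/her last dose of investigational product". Both make it conditional on being possible. Neither states a window, and no section gives a shortest acceptable interval after the last dose.

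A separate visit marks the end of dosing. The table lists it as "End of Treatment Visit (+/- 5 days", and section 5.3 fixes its timing: "Subjects will undergo an End of Treatment Visit at the time of discontinuation of eltrombopag". Every item ticked for the safety visit is also ticked for this one.

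Two other provisions cover the period after stopping:

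- Footnote 2 of the table: "Weekly CBC with differential should be performed weekly for the 4 weeks after discontinuation of eltrombopag".
- SAE rules: section 6.2.2.1 captures SAEs "until 30 days after the last dose of drug unless the participant withdraws consent", and section 6.2.2.3 requires reporting to the study supporter of SAEs during the study or "within 30 days of receiving the last dose of study medication". Both sections also require treatment-related SAEs to be reported after that.

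**The concern.** A window as wide as the interval it is attached to sets no minimum. A safety visit on the day of the last dose meets the table, yet it cannot observe anything that happens after treatment, which is the only reason to hold it separately from the End of Treatment visit.

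The protocol ties adverse event questioning to visits (section 4.1), and its primary safety endpoint is the incidence and severity of all adverse events (section 6.2.2). Section 8.4 says where the adverse event summary starts but gives no post-treatment end. The date of the safety visit therefore largely decides how long a patient is followed for non-serious events after stopping. In a single-arm study of 40 patients, unequal follow-up blurs what an incidence rate means.

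The protocol's own background shows interest in this period. Section 2.3.3 describes a controlled trial in chronic liver disease in which five of six eltrombopag patients with a thrombotic complication had it within 30 days of completing treatment and at a platelet count above 200 × 10⁹/L.

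**Working it through.** The plan derives no figure on this point, so the check is interval arithmetic followed by a comparison of sections. Days are counted from the last eltrombopag dose (day 0). Discontinuation is assumed to fall on about the same day.

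**1. Safety visit window** (section 5.2: nominal day 28, ±28 days)

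- Earliest day: 28 − 28 = 0
- Latest day: 28 + 28 = 56
- Width: 56 − 0 = 56 days

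**2. Overlap with the End of Treatment visit** (sections 5.2 and 5.3: at discontinuation, ±5 days)

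- End of Treatment window: 0 − 5 = −5 to 0 + 5 = +5
- Days in both windows: 0 to 5

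The two visits can fall on the same day. The safety visit can even come first, for example on day 0 with the End of Treatment visit on day 5.

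**3. Comparison with the 30-day SAE period** (sections 6.2.2.1 and 6.2.2.3)

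- The latest permitted visit is 56 − 30 = 26 days after the period ends.
- A visit exactly on day 28 is 30 − 28 = 2 days short of its end. That follows from the nominal day, not from the window.

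**4. What depends on the visit date**

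| Post-treatment information | Protected without the safety visit? |
|---|---|
| SAEs to 30 days, related SAEs later | Yes: 6.2.2.1 and 6.2.2.3 |
| Blood counts for 4 weeks | Yes: footnote 2 |
| Non-serious adverse events | No further scheduled visit elicits them |
| Vital signs, physical examination | No |
| Transfusion assessment | No |
| Liver chemistries | Not clearly (see below) |

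Footnote 1 and section 4.8.3.2 ask for weekly chemistries for 4 weeks after a change in eltrombopag dosing. Neither says that stopping counts as a change. Footnote 1 is attached to the on-treatment column, while footnote 2, which does deal with stopping, names only the CBC. Patients who meet the liver criteria of section 4.8.4 have their own monitoring. For the others, chemistries after stopping rest on the safety visit.

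**5. Other windows in the table**

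The other on-study windows are ±2 days (Cycle 1, Days 8, 15 and 22) or ±5 days (Day 1 of Cycle 2 onwards, and End of Treatment). Screening has a 4-week period, but it precedes treatment and serves a different purpose.

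**6. Illustrative replacements**

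- ±5 days: 28 − 5 = 23 to 28 + 5 = 33. The earliest visit is 23 − 5 = 18 days after the latest End of Treatment visit, and 30 − 23 = 7 days short of the SAE cut-off.
- One-sided, starting at day 30: the earliest visit is 30 − 5 = 25 days after the latest End of Treatment visit and covers the whole 30-day SAE period.

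**The case against.** The best reply is that nobody would hold this visit on day 0. The column names day 28, sections 4.2.1 and 5.4 agree with it, and a visit at discontinuation already exists. The intent is plain, and the ±28 may be a slip. The absence of a window in the two text sections is not a contradiction in itself.

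Much of this is fair. It shows what was probably meant, but it does not alter what the table permits. Nothing in the documents confirms a slip, and a site or monitor judging whether a visit is in window would look at the table.

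A reader might infer that the trial collects no safety information after treatment. The documents do not support that: SAE capture for 30 days is mandatory and weekly blood counts are required for 4 weeks. Nor do they support the inference that an early visit leaves SAEs to spontaneous report. The SAE duties in 6.2.2.1 and 6.2.2.3 apply whatever the visit date, and section 4.1 has adverse events assessed continually. It would also be too strong to call this the only assessment after stopping, because the End of Treatment visit may itself fall up to 5 days later.

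The thrombosis figures in 2.3.3 carry limited weight here. They come from chronic liver disease patients having invasive procedures, and the five events occurred at platelet counts above 200 × 10⁹/L. This trial excludes cirrhosis, and its weekly counts would track platelets after stopping.

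**Conclusion.** The point holds as a minor inconsistency between table and text. As written, the safety visit is in window from day 0 to day 56, overlaps the End of Treatment window on days 0 to 5, and can yield no post-treatment observation. The exposure is confined to non-serious adverse events, examination, vital signs, transfusion assessment and, unless stopping counts as a dosing change, liver chemistries. Visit-based follow-up after stopping could run from 0 to 56 days among compliant patients. How many visits would actually be early cannot be judged from the documents.

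The overlap rests on the last dose and discontinuation being close together. Where eltrombopag is held for some time before it is formally stopped, the two visits are spaced differently.

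The response rate, which is assessed over the first four cycles, the sample size of 40, and the stopping boundaries with their tabulated operating characteristics do not depend on this window.

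**What to change.** In the section 5.2 table, replace the ±28-day window with one that cannot overlap the End of Treatment visit and stays close to the stated 28 days. Two options fit the plan:

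- ±5 days, as for the other late visits, giving days 23 to 33.
- A one-sided window starting at day 30, if the visit is meant to cover the full 30-day SAE period. The nominal timing in the table and text would then change to match.

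Use identical wording in 4.2.1 and 5.4, and keep the existing allowance for patients who cannot attend. The choice between the options belongs to the investigator; the documents require only that the three places agree.

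The cost is one table entry and two matching sentences. A tighter window may produce a few more recorded visit deviations, for example in patients who leave for transplant or are managed partly by outside physicians.

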### 5.3. End of Study Visit:

Subjects will undergo an End of Treatment Visit at the time of discontinuation of eltrombopag. A bone marrow biopsy and/or aspirate with cytogenetics for IPSS and WHO classification will be performed at this visit. Cytogenetics can be omitted if diploid at study start.

### 5.4. Safety Visit:

Whenever possible, subjects will undergo an End of Study Safety Visit 4 weeks after his/her last dose of investigational product in the treatment period.

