### **1.2 Secondary Objectives**

The secondary objectives of the study are:

- To evaluate the safety and tolerability of the combination of eltrombopag and decitabine. Safety will be assessed by the overall incidence and severity of all study-treatment related adverse events per CTCAE v 4.0
- To evaluate the incidence of dose reductions and delays of decitabine therapy
- To evaluate the effect of eltrombopag on medically significant hemorrhagic events (defined as Grade 3 or 4 hemorrhagic events on CTCAE v 4.0)
- To evaluate the effect of eltrombopag on platelet and RBC transfusion independence per IWG-2006 criteria
- Incidence of transformation to AML per FAB criteria (>30% blasts) during treatment period and follow-up
- Incidence and severity of bone marrow fibrosis during treatment period and follow-up
- To examine the relationship between clinical response with ferritin level and other markers of iron burden at study start

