## 8. Statistical Considerations

This is an open label, phase II clinical trial to evaluate the efficacy of eltrombopag in combination with decitabine as a frontline therapy in patients with Intermediate-2 or High-Risk Myelodysplastic Syndrome (MDS). A total of 40 patients will be accrued from M.D. Anderson Cancer Center (MDACC), at a rate of 2-3 patients per month.

The primary endpoint is the overall response rate (ORR) based on the IWG-2006 criteria, which includes complete remission (CR), partial remission (PR), and hematologic improvement (HI). Patients' overall response will be assessed during the first four 28-day cycles of treatment. Patients who drop off the study early due to treatment-related toxicities will be counted as treatment failures (i.e., non-responders).

The method of Thall, Simon and Estey [1995] will be used for futility and toxicity monitoring for this study. The target overall response rate is 60% and the following futility stopping rule will be applied in cohort size of 10, starting from the 10th patient:  $\text{prob}\{p(\text{ORR}) < 0.6\} > 0.95$ , where  $p(\text{ORR})$  denotes the overall response rate. That is, the trial will be stopped early due to futility, if during the study we determine that there is more than 95% chance that the ORR is less than 60%. Assuming that the prior distribution of  $p(\text{ORR})$  is beta (1.2, 0.8), the stopping boundaries corresponding to this futility monitoring rule are shown below in Table 1. The operating characteristics (OCs) for this futility stopping rule are summarized in Table 2. The design software Multic Lean Desktop (version 1.2.0) developed by the Department of Biostatistics at M. D. Anderson Cancer Center (MDACC) was used to generate the futility stopping boundaries and the

OC table. In order to utilize the software for the design, a highly informative beta (600, 400) prior was assumed to approximate the target 60% overall response rate.

Table 1. Futility stopping boundaries in cohort size of 10.

Number of patients	Stop the trial if there are this many patients achieving overall response
10	0-3
20	0-8
30	0-13

Table 2. Operating characteristics for futility monitoring in cohort size of 10 (max sample size = 40).

True ORR	Prob(stop the trial early due to futility)	Average sample size
0.3	0.971	14.8
0.4	0.775	22.0
0.5	0.391	31.3
0.6	0.105	37.5
0.7	0.015	39.6

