## 8.1 Analysis Plan

The primary endpoint is overall response rate (ORR). The ORR will be estimated along with the exact 95% confidence interval. Secondary endpoints include incidence of dose reductions and delays of decitabine therapy, hemorrhagic events (defined as Grade 3 or 4 hemorrhagic events on CTCAE v 4.0), platelet and RBC transfusion independence per IWG-2006 criteria, transformation from MDS to AML, Incidence and severity of bone marrow fibrosis. Descriptive statistics will be used to summarize all secondary endpoints. The incidence rates of binary secondary endpoints will be estimated, along with the exact 95% confidence intervals.

The probabilities of time-to-event outcomes (such as time to transformation from MDS to AML and time to developing BM fibrosis) will be estimated using the method of

Kaplan and Meier. Log-rank tests will be used to compare the time-to-event outcomes among subgroups of patients.

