## 8.3. Analysis of Key Study Endpoints

The primary endpoint is overall response rate (ORR). The ORR will be evaluated along with the exact 95% confidence interval. Secondary endpoints include platelet response, durable platelet response, transformation to AML, incidence of bone marrow fibrosis, and time-to-event outcomes such as progression-free survival (PFS) and overall survival (OS). The probabilities of PFS and OS will be estimated using the method of Kaplan and Meier. The incidence rates of other binary secondary endpoints will be estimated, along with the exact 95% confidence intervals. Subjects that discontinue the study prior to having achieved a clinical response will be considered to have not had an event.

**Patients receiving growth factors other than eltrombopag (erythropoietin, GM-CSF or G-CSF) will not be considered in the HI analysis for the time periods specified in Section 4.5.3 Supportive Care Guidelines. Hemoglobin levels and platelet counts collected from patients that have received a transfusion within the last 7 days will not be considered in the analysis.**

Survival or times to failure and time to progression functions will be estimated using the Kaplan-Meier method. The two-sided log-rank test will be used to assess the differences of time to events between groups.

The total number of dose administrations, the average dose (mg), and the cumulative dose administered will be summarized by eltrombopag treatment group.

Blood chemistry and complete blood counts will be summarized by treatment group at each time point.

Additional exploratory analyses of the key study endpoints will be performed as deemed appropriate.

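### OS, PFS and AML transformation are to be estimated, but no contact is scheduled after the 28-day safety visit and no censoring rule or data cut-off is given

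*Combined protocol and SAP*

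**What the plan says.** **Endpoints.** Section 8.3 lists PFS and OS among the secondary endpoints and states: "The probabilities of PFS and OS will be estimated using the method of Kaplan and Meier". Section 6.2.1 defines OS as death from any cause. Sections 1.2 and 6.2.3 include "Incidence of transformation to AML per FAB criteria (>30% blasts) during treatment period and follow-up", with a parallel item for marrow fibrosis. Section 8.1 applies Kaplan-Meier to "time to transformation from MDS to AML and time to developing BM fibrosis".

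**Last contact.** Section 5.4 says that, where it can be arranged, "subjects will undergo an End of Study Safety Visit 4 weeks after his/her last dose of investigational product in the treatment period". Section 4.2.1 makes the same provision. In section 5.2 the final column is "Safety Visit 28 days after last dose (+/- 28 days" and no later column exists. Weekly blood counts stop 4 weeks after eltrombopag ends. Sections 6.2.2.1 and 6.2.2.3 capture serious adverse events to 30 days after the last dose. After that, capture is essentially limited to events judged related to study treatment.

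**Why patients leave.** Section 4.2.2 lists progression, lack of benefit after 4 cycles, unacceptable toxicity, intercurrent illness, patient decision and possible transplant, among others. Section 4.2.5 sets a usual limit of 12 cycles, which can be extended after discussion with the principal investigator.

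**What is absent.** No section defines the follow-up period, sets a data cut-off, or gives a censoring rule for OS, PFS or AML. The one sentence in 8.3 on discontinuation concerns patients who leave before a clinical response and is not a survival censoring rule.

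**The concern.** Kaplan-Meier is unbiased only if patients censored at a given time have the same outlook as those still observed. Under the schedule as written, observation ends about a month after treatment stops, and most of the listed reasons for stopping plausibly mark a worse outlook. A death or AML transformation three months after stopping has no scheduled route into the data unless it is judged related to study treatment. Chance capture is not assured either: decitabine may be given by local doctors (section 4.3), and the requirement to visit the centre at least every 3 months (section 4.5.1) applies while on study.

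At stake is whether the OS and AML figures describe these patients' course or only the course of those still on treatment. A reader comparing the OS curve with other front-line decitabine series would not see the difference.

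**Working it through.** **Plan's own figures.** The documents give no survival, PFS or AML rate, target event count or follow-up length, so there is nothing to reproduce for these endpoints. The ORR futility design does reproduce (Table 1 exactly; Table 2 at true ORR 0.3: 0.9705 and 14.78, against 0.971 and 14.8 stated). It does not depend on follow-up after stopping.

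**How far the curve can reach.** Twelve cycles take 12 × 28 = 336 days. Adding 28 days gives 364 days, and the far end of the visit window gives 336 + 56 = 392 days. At 30.4 days per month these are 12.0 and 12.9 months. Apart from cycle delays and approved extensions, nobody is observed later than this.

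**Bias in 12-month OS.** All hazards below are assumptions. Times to on-treatment death, to stopping for progression, to stopping for other reasons and to death after stopping are exponential, with 400,000 simulated patients per scenario and no 12-cycle cap. Survival with complete follow-up is compared with Kaplan-Meier censored 28 or 56 days after stopping. Median time to stopping for progression / for other reasons is 12/12 months, except strong (10/12) and mostly favourable (18/6).

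| Scenario (median months to death: on treatment / after progression / after other stop) | Complete follow-up | Censored at day 28 | Censored at day 56 |
|---|---|---|---|
| Mild worsening (30 / 9 / 18) | 0.638 | 0.728 | 0.706 |
| Middle (30 / 6 / 12) | 0.562 | 0.705 | 0.666 |
| Strong (48 / 4.5 / 9) | 0.516 | 0.741 | 0.674 |
| Unchanged (15 / 15 / 15) | 0.574 | 0.575 | 0.574 |
| Mostly favourable (30 / 9 / 60) | 0.750 | 0.752 | 0.749 |

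The smallest excess in the worsening scenarios is 0.706 − 0.638 = 0.068 (7 points). The largest is 0.741 − 0.516 = 0.225 (about 22 points). In the middle scenario about 9 deaths per 40 patients are seen, and in 95% of simulated 40-patient trials the censored 12-month estimate exceeds the complete-follow-up value.

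**Check on direction.** Take death hazard a on treatment, b after stopping, stopping rate g, and censoring at the moment of stopping. Kaplan-Meier then estimates exp(−at), while true survival is

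S(t) = exp(−(a+g)t) + [g/(a+g−b)] × [exp(−bt) − exp(−(a+g)t)].

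- If b = a, this reduces to exp(−at): no bias.
- If every departure were favourable (medians 30 months on treatment, 60 after, 6 to stopping), Kaplan-Meier at 12 months is 2^(−12/30) = 0.758. In units of ln 2, a + g = 1/30 + 1/6 = 0.200 and b = 1/60, so S = 2^(−2.4) + (0.1667/0.1833) × [2^(−0.2) − 2^(−2.4)] = 0.189 + 0.909 × (0.871 − 0.189) = 0.809. The estimate is about 5 points too low.

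**PFS at 12 months.** Assume median 12 months to progression on treatment and 12 months to stopping for other reasons, with censoring at day 28.

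| Median to progression or death after a non-progression stop | Complete follow-up | Censored |
|---|---|---|
| 6 months | 0.424 | 0.485 |
| 4 months | 0.374 | 0.467 |
| 12 months (unchanged) | 0.500 | 0.500 |
| 36 months | 0.575 | 0.510 |

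PFS is 6 to 9 points too high if the hazard rises, unbiased if it is unchanged, and 6 to 7 points too low if it falls.

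**Month 24 without the cap.** In the middle scenario, being at risk at 24 months requires stopping no earlier than 24 − 0.92 = 23.08 months and being alive: 2^(−23.08/6) × 2^(−24/30) = 0.040, or 1.6 of 40 patients. With the usual 12-cycle limit there would be almost none.

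**The case against.** The strongest reply is that the documents never say patients are censored at the safety visit. Sections 1.2 and 6.2.3 name a follow-up distinct from the treatment period, so later observation appears to be intended, and related serious adverse events are still reported after 30 days. This stands: the demonstrable defect is that follow-up and censoring are undefined. It does not remove the problem, because the visit is called the end-of-study visit and nothing is scheduled after it.

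Second, the direction of bias is assumed. Transplant is a listed reason for leaving, and a patient who completes 12 cycles with benefit leaves without a poor prognosis. This stands too, and the range above therefore includes zero and negative values.

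Third, PFS should not be treated like OS. Progression is itself a reason to stop, and section 5.3 requires a marrow at end of treatment, so progression, and AML already present at that point, would mostly be recorded. Only patients who stop for other reasons are exposed. This stands.

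Fourth, OS and PFS are not among the objectives in 1.2 or the key secondary endpoints in 6.2.3. They have no hypothesis or target, and the ORR analysis over four cycles is untouched. This stands and limits the weight of the point.

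**Conclusion.** The gap is real: OS, PFS and AML in follow-up are to be estimated without scheduled follow-up, a cut-off or censoring rules. If patients are censored at the last scheduled contact, censoring depends on the reason for stopping. OS and AML-free estimates are then likely to be optimistic, and PFS less so. For 12-month OS the size is roughly 7 to 22 points too high if prognosis worsens after stopping, nil if it is unchanged, and up to about 5 points too low if departures are favourable. All of these rest on assumed hazards. AML was not simulated; its direction is inferred from the same mechanism.

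A reader might infer that survival will certainly be overstated, or that a large error at 24 months can be quoted. The documents support neither. They state no censoring rule and give no hazards, and the usual 12-cycle limit means the curve would hardly extend past 12 to 13 months. The point concerns secondary, descriptive endpoints. It should be fixed, but it does not threaten the primary analysis.

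**What to change.** 1. In section 5.2, add a row after the safety visit for all treated patients: vital status, AML status, progression status (for those who stopped without progression), and date of subsequent therapy or transplant. Collect it by chart review or telephone every 3 months to a stated data cut-off.
2. In section 8.3, state the censoring rules for OS, PFS and AML, including how transplant is handled in each.
3. If the sponsor does not want this follow-up, remove Kaplan-Meier OS from 8.3 and report AML and progression only as incidence on treatment plus 28 days, labelled as such. Keeping them as Kaplan-Meier curves cut at 28 days would retain the same censoring.

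The cost is a small amount of chart or telephone work for at most 40 patients, with no added procedures or clinic visits. It should be set up prospectively, because unplanned contacts may be hard to recover later. The ORR endpoint, sample size and stopping boundaries do not change.
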